2 ANALYSIS SETS

All eligible subjects will be screened to determine if they meet all inclusion and no exclusion criteria. Subjects who provide informed consent will be considered enrolled in the study. Evaluability of all subjects will be determined before database lock.

2.1 Effectiveness Analysis Sets

There will be two effectiveness analysis datasets for each sub-study: the all-implanted analysis set and the best-case analysis set.

The all-implanted analysis set (AAS) will include all subjects with successful test and comparator article contralateral implantation, with at least one postoperative visit (same postoperative visit for both eyes).

The best-case analysis set (BAS) will include all subjects with successful contralateral implantation with the test and comparator article that had:

- At least one postoperative visit (same postoperative visit for both eyes),
- No preoperative ocular pathology or macular degeneration at any time in either eye, and
- No major protocol deviations

Subjects who become pregnant at any time during the study will also be excluded from the BAS.

The primary analysis set for effectiveness analyses will be the AAS,	
	I

All effectiveness analyses will be conducted on an as-treated basis. Eyes will be categorized under the actual study IOL implanted.

2.2 Safety Analysis Set

The Safety Analysis Set (SAS) will include all eyes with attempted test or comparator article implantation (successful or aborted after contact with the eye). The SAS will be the primary set for all safety analyses.

All analyses for eye-level endpoints (such as ocular adverse events) will be presented separately by lens model. Analyses for subject-level endpoints (such as nonocular adverse events) will be based on the subjects.

Safety analyses will be conducted using the safety analysis set on a treatment-emergent basis. For treatment-emergent safety analyses, eyes will be categorized under the actual test or comparator article implanted (or attempted to implant).

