# 9.6.2 Changes to Treatments/Procedures

In the event an intraoperative exclusion criterion is met during cataract surgery, take appropriate action as described in Table 9-3. The table includes, but is not limited to, the most common or likely complications.

Table 9-3 Procedural Complications

Treatment/Procedure Complication	Precaution(s) and Action(s) to be taken	Subject Status
One or more intraoperative	Do not implant the study	Discontinue subject per Section
exclusion criteria met during 1 st eye surgery; IP did not touch the eye.	IOL. Implant another suitable nonstudy lens per standard of care.	10.4.2.
One or more intraoperative exclusion criteria met during 1 st eye surgery; IP touched the eye.	Do not implant the study IOL. Implant another suitable nonstudy lens per standard of care.	Encourage the subject to remain in the study so as to continue to perform safety assessments only in the 1 st eye, per Section 10.4.3.

Treatment/Procedure Precaution(s) and Complication Action(s) to be take		Subject Status	
		Do not implant the study IOL in the 2 nd eye.	
One or more intraoperative exclusion criteria met during 2 nd eye surgery; IP did not touch the eye.	Do not implant the study IOL. Implant another suitable nonstudy lens per standard of care.	Continue to follow the subject for all safety assessments in the 1 st eye implanted with the study IOL.  Do not perform any assessments on the 2 nd eye.	
One or more intraoperative exclusion criteria met during 2 nd eye surgery; IP touched the eye.	Do not implant the study IOL. Implant another suitable nonstudy lens per standard of care.	Continue to follow the subject for all safety assessments in the 1 st eye, implanted with the study IOL.  Continue to perform safety assessments only on the 2 nd eye, per Section 10.4.3.	

NOTE: A nonstudy lens is defined as a lens that the clinic has procured on its own (all lenses provided by Alcon for this study (for both the test group and comparator group) are considered in the category of 'study lens').

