# 10.4.3 Subjects with Aborted Implantation and Explanted IOL(s)

Implantation may be attempted twice. After two aborted attempts to implant, meaning the investigational product touched the eye, the eye must be implanted with a nonstudy provided IOL. Refer to Section 9.6.2 for additional information.

If the IOL implantation is attempted and aborted due to device deficiency, then a device deficiency form must be completed and the IOL must be returned to the study sponsor in appropriate safe packaging.

In case an explant is performed: the explanted eye will be followed for safety as routine standard of care for explants of approved IOLs.

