5.3.1 Adverse Events

The applicable definition of an AE is in the study protocol. All AEs occurring from when a subject signs informed consent to when a subject exits the study will be accounted for in the reporting.

Descriptive summaries (counts and percentages) for AEs will be presented by Preferred Term.

Adverse events will be summarized in the following tables:

- 1. Overall Summary of Treatment-Emergent Adverse Events
- 2. All Adverse Events (Serious and Nonserious Combined)
 - a. Ocular
 - b. Nonocular
- 3. All Serious Adverse Events (including Serious Adverse Device Effects)
 - a. Ocular
 - b. Nonocular
- 4. Subject Listings
 - a. All Ocular
 - b. All Nonocular

In addition, listings of AEs that occur after signing informed consent but prior to exposure to investigational product will be provided separately for ocular and nonocular AEs.

Secondary surgical interventions (SSIs) will be summarized descriptively (counts and percentages) and will be presented separately by lens model in each of the following categories:

- Any
- Related to IOL due to optical properties
- Related to IOL not due to optical properties
- Unrelated to IOL

Additionally, descriptive summaries (counts and percentages) for SSIs will be presented by Preferred Term. Confidence intervals/limits will be presented as applicable.

A listing of all SSIs will also be provided.

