5.3.5 Subjective Posterior Capsule Opacification (PCO)

Assessment

The number and percentage of eyes representing the maximum rating for an eye during the study will be tabulated by the response categories presented on the CRF (i.e., none, clinically nonsignificant, clinically significant, clinically significant requiring a YAG) and summarized by lens model. Similarly, eyes with a 'worst case' rating of clinically significant PCO or posterior capsulotomy (YAG) will be summarized by the response categories on the CRF.

A listing of eyes with clinically significant PCO, clinically significant PCO requiring YAG, or posterior capsulotomy will be presented which includes the PCO or capsulotomy results at all visits.

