5.3.6 Posterior Capsulotomy

The number and percentage of eyes with posterior capsulotomy (overall and by reason) will be tabulated by lens model.

5.3.7 **IOL Observations**

The number and percentage of IOL observations reported at each scheduled visit will be tabulated by lens model. A listing of all IOL observations will also be provided.

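### Eyes touched by a study IOL but left with a nonstudy lens are counted under the study model in the PCO, capsulotomy and IOL observation tables

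*SAP*

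**What the plan says.** SAP 2.2 defines the SAS as "all eyes with attempted test or comparator article implantation (successful or aborted after contact with the eye", and for treatment-emergent safety analyses "eyes will be categorized under the actual test or comparator article implanted (or attempted to implant". SAP 5.3 uses this set for every safety analysis unless a section says otherwise.

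The Protocol says which lens an aborted eye receives. In Table 9-3 (section 9.6.2), when an intraoperative exclusion is met, the action is "Do not implant the study IOL. Implant another suitable nonstudy lens per standard of care". In the two rows where the product touched the eye, safety assessments of that eye go on; for a first eye, the subject is encouraged to stay in the study for them. Section 10.4.3 adds that after two aborted attempts with contact, "the eye must be implanted with a nonstudy provided IOL".

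Three SAP sections then report by lens model with no restriction to eyes that hold that model:
- 5.3.5, PCO: "The number and percentage of eyes representing the maximum rating for an eye during the study will be tabulated", by CRF category and lens model.
- 5.3.6, capsulotomy: number and percentage of eyes, overall and by reason, by lens model.
- 5.3.7, IOL observations: "The number and percentage of IOL observations reported at each scheduled visit will be tabulated by lens model".

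**The concern.** Filing an aborted eye under the attempted lens makes sense where the attempt itself can cause the outcome: adverse events, IOP, surgical problems, device deficiencies. It fits poorly where the outcome describes the lens that stays in the eye or the capsule behind it. Haze or discoloration recorded as an IOL observation in such an eye is a finding on a lens that is not a study product. PCO and later capsulotomy develop behind that same lens.

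As written, the finding is credited to a study model. If the eye has no finding, it still sits in that model's denominator, where it could not have shown a finding of that lens. Safety has no hypotheses here, so the by-lens percentages are the result that readers will use.

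**Working it through.** **Which eyes are affected**

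1. Product did not touch the eye: outside the SAS. Not affected.
2. Product touched the eye, the first attempt was aborted, and a study lens was then implanted: filed under the lens in the eye. Not affected.
3. Product touched the eye and a nonstudy lens was implanted (Table 9-3 touched rows, or two aborted attempts under 10.4.3): in the SAS under the attempted model. Affected, if follow-up continues.

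**Do the three outcomes get recorded in those eyes?** Protocol 10.2.32 to 10.2.34 label IOL observations, PCO and capsulotomy as safety assessments. Table 3-1 schedules PCO and IOL observations at every postoperative visit and capsulotomy as needed. Table 9-3 continues safety assessments in touched eyes. On that reading, yes.

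**Is the primary analysis affected?** No. The all-implanted set (SAP 2.1) requires successful implantation of test and comparator lenses in both eyes, so an eye of type 3 removes its subject from that set.

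**Size.** The plan gives no figure for this point. The denominator comes from Protocol 12.8 and SAP 7: 132 / 2 = 66 subjects per sub-study, each planned to have one eye per model, so about 66 eyes per model.

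Let N = 66 SAS eyes filed under one model, k = those holding a nonstudy lens (an assumption), x = study-lens eyes with the finding, and y = nonstudy-lens eyes with the finding, between 0 and k.

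- Rate as the SAP is written: (x + y) / N
- Rate in eyes that hold the lens: x / (N − k)
- Share of the denominator: k / N, which is 1/66 = 1.5%, 2/66 = 3.0% and 3/66 = 4.5% for k = 1, 2, 3

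| k | x | Eyes holding the lens | As written, y = 0 | As written, y = k |
|---|---|---|---|---|
| 1 | 0 | 0/65 = 0% | 0/66 = 0% | 1/66 = 1.5% |
| 2 | 2 | 2/64 = 3.1% | 2/66 = 3.0% | 4/66 = 6.1% |
| 3 | 3 | 3/63 = 4.8% | 3/66 = 4.5% | 6/66 = 9.1% |

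Dilution (y = 0) is negligible. The visible effect is in the other direction: one affected eye with a finding can turn a true 0% into 1.5%. If 66 is instead the number successfully implanted, aborted eyes add to it and the shares fall slightly, for example 3/69 = 4.3%. With k = 0 nothing changes.

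**How much of this data will exist?** Protocol 10.4.1 withdraws subjects found no longer eligible for a study lens after randomization, and names intraoperative exclusions as a reason. Table 9-3 keeps subjects with a touched eye in safety follow-up. Both cannot hold for the same subject, and the choice between them determines k.

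**The case against.** **Attribution to the attempted device is a standard, conservative safety convention.** It avoids exclusions made after surgery, and PCO also depends on the surgery. This stands for the general safety tables, which should keep the full SAS. It does not make a finding on a nonstudy lens informative about a study model.

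**The reader can trace the eyes.** SAP 3.1 counts attempted and successful implantations. SAP 5.3.5 and 5.3.7 plan listings of eyes with clinically significant PCO or capsulotomy and of all IOL observations. This helps, but it does not correct the by-lens percentages, and the SAP does not say that the listings identify the lens in the eye.

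**The effect may be tiny or absent.** This stands. No abort rate is given, the larger shifts require every affected eye to have the finding, and safety is descriptive.

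A reader might also infer more than the documents support:

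- *That the same happens after an explant or exchange.* The SAP sets no cut-off at explant, and the PCO table takes the worst rating over the study. But Protocol 10.4.3 moves explanted eyes to routine standard-of-care follow-up, and nothing says that study PCO grading or IOL observations continue in them.
- *That optical SSIs from a nonstudy lens are charged to the study model.* SAP 5.3.1 has a category "Related to IOL due to optical properties" but does not say which IOL is meant. Protocol 11.4 handles events of nonstudy marketed products as spontaneous reports to their manufacturer. The text does not settle it.
- *That these tables are the trial's only device-specific safety results.* They are not: SAP 5.3.2 tabulates device deficiencies by lens model.

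**Conclusion.** The point holds for three tables: PCO, capsulotomy and IOL observations. It follows from stated rules rather than from silence, because SAP 2.2 assigns the eye to the attempted lens, SAP 5.3 carries that set into every safety table, and 5.3.5 to 5.3.7 do not depart from it.

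Each affected eye is about 1.5 percentage points of a roughly 66-eye denominator. It can raise a reported rate by up to about that much, or dilute it slightly. This rests on two assumptions: that at least one touched eye ends with a nonstudy lens and stays in follow-up, and that about 66 eyes are filed per model. The results concerned are descriptive, and the primary conclusion does not depend on them. This is an inexpensive improvement in accuracy and does not threaten the trial.

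**What to change.** In SAP 5.3.5, 5.3.6 and 5.3.7, base the by-lens percentages, numerator and denominator alike, on SAS eyes with a successfully implanted study IOL. List findings in aborted eyes that hold a nonstudy lens separately, and name the model that was attempted. Keep the full SAS, with attribution to the attempted lens, for AEs, SSIs, IOP, surgical problems and device deficiencies.

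Reconcile Protocol 10.4.1 with Table 9-3, so that it is clear whether a subject with a touched eye and no study lens in that eye is withdrawn or followed.

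The cost is a sentence in each of three SAP sections and one subset flag. The CRF is not among the documents, but the disposition table in SAP 3.1 already has to separate attempted from successful implantation, so the information should be at hand. The downside is slightly smaller denominators in three tables, which will then differ from the SAS count and need a footnote.

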3 SUBJECT CHARACTERISTICS AND STUDY CONDUCT SUMMARIES

Subject characteristics and study conduct summaries include tables and/or listings for subject disposition, demographics, and baseline characteristics, targeted medical history and concomitant medications, baseline eye biometry, baseline monocular visual acuity and manifest refraction spherical equivalent (MRSE), and surgical summary. All descriptive summary statistics will be displayed with number of subjects/eyes and percentage for categorical data, and with number of subjects/eyes, mean, standard deviation (SD), median, minimum, and maximum for continuous data. Tables will be presented by lens model (PXYWT0 (or PAYWT0) and CNWTT0) or total subjects as applicable.

Baseline will be defined as the last measurement prior to exposure to investigational product, except otherwise stated.

Subject characteristics and study conduct summaries will be presented on the AAS and SAS. Subject characteristics and study conduct summaries will be presented on the BAS if the number of eyes excluded from the BAS exceeds 10% of the AAS.

3.1 Subject Disposition and Study Conduct

A subject disposition table will be presented that displays the number of subjects enrolled in the study, in addition to the number of screen failures, the number randomized, the number with attempted implantation, successful implantation, completed study, and discontinued

study. This table will also contain counts for each reason for premature study discontinuation. Corresponding listings of reasons for early study discontinuation will also be provided separately for discontinuations prior to attempted implantation (including screen failures) and for discontinuations after attempted implantation.

Accountability at each postoperative visit will be presented for AAS and SAS (BAS if applicable) for each lens model. Accounting at each postoperative visit will also be presented for the primary effectiveness endpoint (i.e., monocular photopic BCDVA) for AAS and BAS by lens model.

Summaries of subject eye evaluability for each analysis set will be provided by lens model and by subject.

In addition, summary tables or listings will be provided including:

- Number of subjects treated by investigator
- Lens model assignment (including demographics (see below) and study exit status)
- Eyes receiving lens model different than planned
- Subject eyes excluded from analysis and/or from study
- Protocol deviations

3.2 Demographics

Demographics will be summarized by the number and percentage of subjects for the categorical variables, and descriptive statistics (number of subjects, mean, SD, median, minimum, and maximum) for the continuous variables based on AAS and SAS (BAS if applicable).

Demographics (subject-level)

Categorical variables:

- Sex (Female, Male, Unknown, Undifferentiated)
- Race (per Case Report Form (CRF))
- Ethnicity (per CRF)

Continuous variable:

• Age (years)

3.3 Medical History and Concomitant Medications

Targeted medical history and concomitant medications will be listed for all subjects based on the SAS.

Medical history includes the subject's full ocular history and targeted systemic history at screening visit; and concomitant medications include all ocular and nonocular medications taken within 30 days prior to the informed consent date.

3.4 Baseline Eye Biometry

Assessments of eye biometry will be summarized preoperatively by descriptive statistics (number of eyes, mean, SD, median, minimum, and maximum) for continuous variables by lens model. Assessments will be presented based on AAS and SAS (BAS if applicable). Continuous variables:

- Axial length (mm)
- Anterior chamber depth (mm)
- Corneal astigmatism (D) = abs (K1-K2)

3.5 Baseline Visual Acuity and MRSE

Baseline visual acuity and MRSE will be summarized preoperatively using descriptive statistics (number of eyes, mean, SD, median, minimum, and maximum) for continuous variables by lens model. Results will be presented based on AAS and SAS (BAS if applicable).

Continuous variables:

- Monocular photopic BCDVA (logMAR)
- Monocular MRSE (D) = sphere + $\frac{1}{2}$ cylinder

3.6 Surgical Summary

Surgical factors will be summarized by descriptive statistics (number of eyes, mean, SD, median, minimum, and maximum) for continuous variables by lens model. Results will be presented based on AAS.

Continuous variables:

- Target residual refractive error (TRRE) (D)
- Predicted residual astigmatism (D)
- Lens power (D) (Median, Min, Max only)

4 EFFECTIVENESS ANALYSIS STRATEGY

The protocol defines 1 primary	effectiveness endpoint for each
sub-study. Within each sub-study, a success on the pa	rimary effectiveness endpoint would be
indicated by achieving noninferiority of the Clareon	PanOptix Pro model IOLs to the Clareon
PanOptix IOLs in mean monocular photopic BCDV	A at 2 months postoperative.

All effectiveness endpoints will be summarized descriptively according to the type of parameter (i.e., whether data are categorical or continuous) being analyzed. For categorical variables, the descriptive statistics will include number of observations, count in the category, and percent in the category. For continuous variables, the descriptive statistics will include number of observations, mean, median, standard deviation, standard error, minimum, and maximum. Confidence intervals will be provided as applicable. Summaries of continuous endpoints will also include mean differences between lens models and associated descriptive statistics.

Unless otherwise specified, effectiveness endpoints will be summarized by lens model at the postoperative scheduled visits.

All data obtained in evaluable subjects/eyes will be included in the analysis. Missing data will not be imputed.

4.1 Effectiveness Endpoints – Sub-Study A

Primary Effectiveness Endpoint

Mean monocular photopic BCDVA (logMAR) at 4 m at 2 months postoperative (Visit 3A)

4.1.1 Effectiveness Hypotheses

Primary Effectiveness

The null and alternative hypotheses to be evaluated in support of the primary noninferiority objective are as stated below:

$$H_0: \mu_D \geq \Delta$$

 $H_a: \mu_D < \Delta$

where, Δ refers to the noninferiority margin, set at 0.1 logMAR, and μ_D refers to the mean of the difference between paired observations of each subject's eyes (test minus comparator) for monocular photopic BCDVA at 2 months post implantation.

4.1.2 Statistical Methods for Effectiveness Analyses

Table 4-1 summarizes the primary Supportive analyses using the BAS will be conducted only if the number of eyes excluded from the BAS exceeds 10% of the AAS.

Table 4-1 Sub-Study A – Summary of Analysis Strategy for Primary

Endpoint	Main vs. Supportive	Comparison/	Analysis	Missing
1	Approacha	Statistical	Set	Data
		Method		Approach
Primary				
Mean monocular photopic BCDVA (logMAR) at 4 m	M	One-sample t-test for noninferiority	AAS	Observed data only
at 2 months postoperative (Visit 3A)	S		BAS	

Primary Effectiveness Analyses

The primary effectiveness endpoint, associated with the above hypotheses, will be tested by generating a one-sided 95.1% upper confidence limit based on the mean paired difference (Clareon PanOptix Pro – Clareon PanOptix) using a one-sample t-test. The upper bound of the one-sided 95.1% confidence limit will be compared to the margin, 0.10 logMAR. If the upper bound is less than the margin, the null hypothesis will be rejected, and it will be concluded that Clareon PanOptix Pro is non-inferior to Clareon PanOptix for monocular photopic BCVDA at 4 m. The difference in means (Clareon PanOptix Pro minus Clareon PanOptix), standard error, and the associated one-sided 95.1% upper confidence limit will be presented.

4.2.1 **Effectiveness Hypotheses**

Primary Effectiveness

The null and alternative hypotheses to be evaluated in support of the primary noninferiority objective are as stated below:

$$H_0: \mu_D \ge \Delta$$

 $H_a: \mu_D < \Delta$

where, Δ refers to the noninferiority margin, set at 0.1 logMAR, and μ_D refers to the mean of the difference between paired observations of each subject's eyes (test minus comparator) for monocular photopic BCDVA at 2 months post implantation.

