# 12.8 Sample Size Justification

A total of 132 subjects will be randomized (approximately 66 per sub-study). Assuming a drop-out rate of 10%, approximately 60 subjects will be evaluable at 2 months postoperative period (visit 3A) for each sub-study. The power estimates for each of the planned analyses are presented below:

Order	Endpoint	Comparison	Expected difference	Std. Dev^	Power	
Sub-study A						
Primary	Monocular BCDVA	NI	0	.08	>99.9%	
Sub-study B						
Primary	Monocular BCDVA	NI	0	.08	>99.9%	

Primary Monocular BCDVA NI 0 .08 >99.9%

^Estimate of std. dev is based on two recent Alcon studies (ILH297-C001 and ILI875-C002). \* Estimated based of simulated results from VirtIOL. \*\*Difference would indicate clinically meaningful effect. A NI margin of 0.1 logMAR is used for all non-inferiority comparisons above.

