1.3 Randomization

Only after signing the informed consent form (ICF), a subject will be assigned a subject number by the electronic data capture system (EDC). Lens model will be assigned by randomization via the EDC system on the day of or after the Screening visit if the subject meets all entry criteria.

Subjects will be randomized to one of two sub-studies and to contralateral lens model in a 1:1 ratio. Subjects will be block randomized by investigational site. Subjects at each site will be randomized to one of two sub-studies in a 1:1 ratio. Sub-study A will evaluate Model PXYWT0, and sub-study B will evaluate Model PAYWT0. Subjects randomized to sub-study A will be further randomized to receive Model PXYWT0 or Model CNWTT0 in the first surgical eye, and the second eye will receive the other lens. Similarly, subjects randomized to sub-study B will be further randomized to receive Model PAYWT0 or Model CNWTT0 in the first surgical eye and the second eye will receive the other lens. The 1st surgical eye will be the eye with the worse BCDVA at screening. When the BCDVA is equal between the two eyes, the right eye (OD) will be the 1st surgical eye.

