1.5 Interim Analysis

Two interim analyses are planned for this study.

The first interim analysis will be conducted when approximately 40 subjects (approximately 20 in each sub-study, minimum 30 subjects total) complete the 2-Month postoperative visit. This interim analysis is designed to review preliminary safety and effectiveness results for strategic business decision making purposes. There is no intention of stopping the study early. A second interim analysis will be conducted when all subjects complete the 2-Month postoperative visit, at this point treatment arms will be unmasked, and all inferential analysis will be conducted. To control the overall type I error rate (at one-sided alpha = 0.05) the Lan-DeMets method with an O'Brien-Fleming alpha spending function will be utilized to distribute the type I error rate between the first and second interim analyses. The first interim analysis will be conducted when approximately 1/3 of the information fraction (in this case 1/3 of the target sample size) is available, therefore for administrative purposes a one-sided alpha of approximately 0.001 will be spent at the first interim analysis and accordingly the

significance level at the second interim analysis (which is the primary inferential analysis point) will be one-sided 0.049 for all effectiveness endpoints. The power estimates provided below are based on a one-sided 0.049 significance level.

A final analysis will be performed once the 6-Month follow-up is complete, at which time the study database will be considered final and locked to report longer term effectiveness and safety results.

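### The primary noninferiority t-test is valid but makes no use of the screening BCDVA already collected in both eyes; a prespecified regression could sharpen the limit slightly

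*SAP*

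**What the plan says.** SAP 4.1.2 and 4.2.2, and Protocol 17.1.2 and 18.1.2, describe the same primary test. It works by "generating a one-sided 95.1% upper confidence limit based on the mean paired difference"; in full, the limit is "based on the mean paired difference (Clareon PanOptix Pro – Clareon PanOptix) using a one-sample t-test". That one-sided upper limit is set against 0.10 logMAR. No covariate is named.

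The endpoint measure also exists before surgery. Protocol Table 3-1 schedules monocular photopic BCDVA at Visit 0, and Protocol 10.2.15 defines it as ETDRS at 4 m in each eye by a masked assessor. Every randomised subject needs the value, because SAP 1.3 states: "The 1st surgical eye will be the eye with the worse BCDVA at screening". The lens given to that eye is then randomised 1:1, in blocks by site.

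The only visible analysis of the screening value is in SAP 3.5: "Baseline visual acuity and MRSE will be summarized preoperatively using descriptive statistics".

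On size, Protocol 12.8 gives an expected difference of 0, an SD of 0.08 and power above 99.9% ("Primary Monocular BCDVA NI 0 .08 >99.9"%). It adds "A NI margin of 0.1 logMAR is used for all non-inferiority comparisons above" and "Estimate of std. dev is based on two recent Alcon studies". SAP 1.5 sets the level: "The power estimates provided below are based on a one-sided 0.049 significance level".

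**The concern.** Pairing removes variation between subjects. It does not remove variation that comes from one eye of a subject starting worse than the other. Randomising the lens to the first (worse) or second (better) eye balances how often the worse eye gets the test lens. It does not balance how large the gap between the eyes is, and the analysis never uses that gap.

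If part of the screening gap persists after surgery, two things follow. It adds noise to the paired difference and so pushes the upper limit away from the estimate. And when the larger gaps fall by chance on one lens, the point estimate moves with them. SAP 3.5 would display such an imbalance, but the visible text gives no prespecified way to account for it. What is at stake is the precision of the reported limit, not the validity of the test.

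**Working it through.** **Inputs from the documents.** 66 subjects per sub-study with 10% dropout: 66 × 0.9 = 59.4, which the plan takes as about 60 pairs. Margin 0.10, true difference 0, SD 0.08, one-sided alpha 0.049. Protocol 12.8 does not say whether 0.08 is the SD of the paired difference or of a single eye, so both readings were tried.

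**Input not in the documents.** r, the correlation between the screening and Visit 3A paired differences (test minus comparator). It is an assumption and is shown over a range.

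**1. The plan's own figure.** One-sample t-test, noncentral t, 59 df.
- SD of the difference 0.08: SE = 0.08/√60 = 0.0103; power above 99.9999%.
- 0.08 per eye with uncorrelated eyes: SD of the difference = 0.08 × √2 = 0.113; SE = 0.0146; power 99.99998%.

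Both agree with the stated figure of more than 99.9%.

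**2. Distance from estimate to limit, unadjusted.** t(0.951, 59) × SE = 1.681 × 0.0103 = 0.0174. The test passes for any observed difference up to 0.100 - 0.0174 = 0.083. With SD 0.113, that bound is 0.075.

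**3. Adjusted, by formula.** The SE becomes approximately SE × √(1 - r²), with 58 df.
- r = 0.3: 0.0103 × 0.954 = 0.0099; distance 0.0166.
- r = 0.5: 0.0103 × 0.866 = 0.0089; distance 0.0150.

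**4. Adjusted, by simulation.** The formula ignores the cost of estimating the slope, so trials of 60 pairs were simulated with the worse eye first and total SD 0.08. The screening-difference SD was taken as 0.20; its scale cancels from the percentages. The regression intercept (58 df) was compared with the t-test (59 df). Lens order was either split exactly 30/30 or assigned 1:1 without constraint. Blocking by site, with dropout, should fall between the two.

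| r | Change in distance, exact 30/30 | Change in distance, unconstrained 1:1 |
|---|---|---|
| 0 | +0.3% | +0.9% |
| 0.1 | -0.2% | +0.4% |
| 0.2 | -1.7% | -1.2% |
| 0.3 | -4.3% | -3.8% |
| 0.5 | -13% | -13% |

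**5. What the narrowing consists of.** With an exact 30/30 split, the t-test ignores balance that the design has already created, so its limit is conservative. At a true difference of 0.10 its rejection rate is roughly 0.045 at r = 0.3 and 0.035 at r = 0.5, against a nominal 0.049. The regression stays near 0.049. Much of the narrowing in the middle column therefore corrects that conservatism. The true sampling SD of the estimate falls by only about 1.4% at r = 0.3 and 5% to 6% at r = 0.5. With unconstrained assignment, both methods hold about 0.048 to 0.050, and the sampling SD falls by about as much as the distance does.

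**6. Movement of the estimate.** With exact balance, adjustment moves the estimate by a mean absolute 0.0010 logMAR at r = 0.2 and 0.0025 at r = 0.5. At r = 0, where there is nothing to correct, it still moves it by 0.0005 (0.0009 unconstrained). A large part of the figure at r = 0.2 is therefore noise from estimating the slope.

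**7. Effect on the decision.** At a true difference of 0, power exceeds 99.9% for every r from 0.1 to 0.7. At a true difference of 0.07 (by formula):
- SD 0.08: 88.8% unadjusted, 91.2% at r = 0.3, 95.1% at r = 0.5.
- SD 0.113: 64.6% unadjusted, 68.2% at r = 0.3, 75.5% at r = 0.5.

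**The case against.** The strongest reply is that nothing is wrong. The hypotheses concern the mean paired difference, and a one-sample t-test addresses that directly. The lens for the worse eye is randomised, so a chance imbalance is already covered by the confidence limit. That stands. A reader might infer that the primary estimate is biased or the test invalid; the documents do not support this.

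A reader might also infer that the between-eye variation is predictable from screening. The documents do not show that either. Screening acuity is measured through a cataract that is then removed. Protocol 8.1 requires potential postoperative BCDVA of 0.2 logMAR or better in each eye. Protocol 8.2 excludes amblyopia and a long list of corneal, retinal and optic nerve conditions. All of this points to a low r, where the gain is close to nothing. This stands too, and it is why the result is given from r = 0 upward.

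The regression also has its own conditions. Its intercept equals the target mean only if the relation is linear and the expected screening difference is zero. Randomisation secures the second condition for all randomised subjects. The primary set, though, is as-treated and limited to subjects with both lenses successfully implanted and a postoperative visit. The reliance is mild but real.

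Finally, text around SAP Tables 4-1 and 4-2 is missing from the public copy, so a supportive adjusted analysis cannot be ruled out. The primary method itself is fully visible.

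**Conclusion.** The point holds as a small, optional gain in precision. The primary test is valid but leaves unused a baseline measure of its own endpoint that every randomised subject must have.

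The size depends on an r that the documents do not give. The distance of 0.0174 logMAR grows by up to about 1% if r is zero, is practically unchanged at 0.1, and shrinks by 1% to 2% at 0.2, 4% at 0.3 and 13% at 0.5. At r = 0.3 that is 0.0174 - 0.0166 = 0.0008 logMAR against a margin of 0.10. If lens order is exactly balanced, the real gain in sampling precision is smaller than the narrowing of the limit. The percentages do not depend on which reading of the SD is right.

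It would be too strong to say that noninferiority is in doubt without adjustment. Power is above 99.9% with or without it, and the conclusion could plausibly differ only if the true difference were close to the margin.

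**What to change.** In SAP 4.1.2 and 4.2.2 (with Tables 4-1 and 4-2) and Protocol 17.1.2 and 18.1.2, specify a linear regression of each subject's Visit 3A paired BCDVA difference on the screening paired difference. Both are test eye minus comparator eye, and the covariate is not mean-centred. Take the intercept as the estimate of the mean difference and compare its one-sided 95.1% upper limit with 0.10 logMAR. Keep the unadjusted t-test as a sensitivity analysis. Hypotheses, margin, alpha and analysis set stay as they are.

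Fix this before any unmasked primary results are seen. SAP 1.4 lets sponsor personnel be unmasked to the first-interim subset, so the safe point is before that lock.

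The cost is a few sentences, one model statement and no new data. Changing the protocol appendices would need an amendment under Protocol section 4. If the sponsor does not want that for so small a gain, naming the same regression in the SAP as a supportive analysis would still give a prespecified answer to any screening imbalance. The statistical downside is a limit up to about 1% wider if screening acuity proves unrelated to the outcome, plus the mild model reliance noted above.
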